8.1.7 Administration

Nivolumab injection is to be administered as an IV infusion, using a volumetric pump with a 0.2 / 0.22 micron pore size, low-protein binding polyethersulfone membrane in-line filter at the protocol-specified doses.

8.1.8 Ordering

Nivolumab will be obtained from Bristol Myers Squibb (BMS) as an Investigator Initiated Study. Nivolumab can be ordered from BMS by providing a completed Drug Shipment Form.

8.1.9 Accountability

The investigator, or a responsible party designated by the investigator, should maintain a careful record of the inventory and disposition of the agent using the NCI Drug Accountability Record Form (DARF) or another comparable drug accountability form. (See the NCI Investigator's Handbook for Procedures for Drug Accountability and Storage.)

8.1.10 Destruction and Return

At the end of the study, unused supplies of Nivolumab should be destroyed according to institutional policies. Destruction will be documented in the Drug Accountability Record Form.

8.2 Ipilimumab

8.2.1 Description

Ipilimumab is a fully human monoclonal immunoglobulin G1κ antibody that targets the human cytotoxic T lymphocyte antigen 4 (CTLA-4) cell surface membrane receptor.

8.2.2 Form

Ipilimumab Injection Drug product is a sterile, non-pyrogenic, single-use, isotonic aqueous solution formulated at 5 mg/ml (0.9% sodium chloride injection; USP, or 5% dextrose injection). The solution is a clear to slightly opalescent colorless to pale yellow liquid and may contain a small amount of translucent-to-white particles. BMS will provide 50mg/10ml or 200mg/40mL vials for this study.

8.2.3 Storage and Stability

Ipilimumab must be stored at 2°-8°C (36°-46°F) and protected from light and freezing. Partially used vials should be discarded after single use.

8.2.4 Compatibility

Ipilimumab will not be mixed with any other study agents.

8.2.5 Handling

Vials containing Ipilimumab should not be shaken and should be discarded if cloudy.

8.2.6 Availability

In this protocol, Ipilimumab is an investigational product and will be supplied by Bristol Myers Squibb to the participating institution's pharmacy.

At the end of the study period, Bristol-Myers Squibb Company will not continue to supply Ipilimumab to subjects/investigators unless the Sponsor-Investigator chooses to extend their study. The investigator is responsible to ensure that you receive appropriate standard of care or other appropriate treatment in the independent medical judgement of the Investigator to treat the condition under study.

8.2.7 Preparation

Ipilimumab will be used directly from the supplied vial; no further dilution will be required.

8.2.8 Administration

The specified volume of Ipilimumab will be drawn directly into a syringe from the supplied vial. The needle for withdrawal from the vial will be removed and replaced with a needle for subcutaneous injection. Filled syringes should be used for injection as soon as possible after preparation.

8.2.9 Ordering

Ipilimumab will be obtained from Bristol Myers Squibb (BMS) as an Investigator Initiated Study. Ipilimumab can be ordered from BMS by providing a completed Drug Shipment Form.

8.2.10 Accountability

The investigator, or a responsible party designated by the investigator, should maintain a careful record of the inventory and disposition of the agent using the NCI Drug Accountability Record Form (DARF) or another comparable drug accountability form. (See the NCI Investigator's Handbook for Procedures for Drug Accountability and Storage.)

8.2.11 Destruction and Return

At the end of the study, unused supplies of Ipilimumab should be destroyed according to institutional policies. Destruction will be documented in the Drug Accountability Record Form.

8.3 Poly-ICLC (Hiltonol®)

8.3.1 Description

8.3.2 Form

Poly-ICLC is supplied by Oncovir in single-dose vials containing 1 mL of 1.8 mg/mL opalescent white suspension. Each milliliter of poly-ICLC for injection contains 1.8 mg/mL poly-IC, 1.5 mg/mL poly-L-lysine, and 5 mg/mL sodium carboxymethylcellulose in 0.9% sodium chloride solution, adjusted to pH 6-8 with sodium hydroxide.

8.3.3 Storage and Stability

Poly-ICLC is normally shipped or stored refrigerated at about 40°F (2-8°C) but should not be frozen. Based on extended formal stability data at +5°C ± 3°C and at +25°C ± 2°C, it is justified to accept temperature excursions during transport, shipment and storage of Hiltonol® at clinical sites up to +27°C for up to 5 days. Likewise, temperature deviations between 0°C and +2°C are acceptable and have no effect on product quality.

8.3.4 Compatibility

Poly-ICLC will be mixed with personalized neoantigen peptides just prior to use to prepare the final product (NeoVax plus Montanide).

8.3.5 Handling

There are no specific handling instructions for poly-ICLC.

8.3.6 Availability

Poly-ICLC is an investigational agent and has been purchased from Oncovir, Inc. under a Clinical Trials Agreement between DFCI and Oncovir, Inc, dated May 2012. Under that agreement Oncovir, Inc will grant access to the Drug Master File for poly-ICLC for regulatory purposes and provides DFCI information necessary to pursue the clinical use of poly-ICLC. Vials of poly-ICLC sufficient for this clinical trial will be shipped from the Hiltonol® storage facility (Bellwyck Packaging, Mississauga, Ontario, Canada) to the DFCI Pharmacy. Poly-ICLC can be ordered directly from Oncovir, Inc, by submitting a purchase order to:

Oncovir, Inc.

8.3.7 Preparation

Poly-ICLC is supplied as an opalescent white suspension. It will be directly withdrawn from the vial under sterile conditions and mixed with the personalized neoantigen peptides (see Section 8.4.7).

Upon allowing the vial to reach room temperature (approximately 1-2 hours), the vial should be gently inverted about 10 times to insure suspension of the formulation. Gently tap the vial to gather the liquid suspension to the bottom of the vial to aid in extracting the required volume for dose preparation. If visible particulates or aggregates are present when measured against a black background and are not resuspendable or the settled material fails to re-suspend, the vial should be placed in quarantine and not used for clinical administration. Obtain a new vial of Poly-ICLC for dosage preparation.

8.3.8 Administration

Following mixing with the personalized neoantigen peptides, the vaccine (peptide + poly-ICLC + Montanide) is to be administered subcutaneously.

8.3.9 Accountability

The investigator, or a responsible party designated by the investigator, should maintain a careful record of the inventory and disposition of the agent using the NCI Drug Accountability Record Form (DARF) or another comparable drug accountability form. (See the NCI Investigator's Handbook for Procedures for Drug Accountability and Storage.)

8.3.10 Destruction and Return

At the end of the study, unused supplies of poly-ICLC will be held by the IND holder for future use until they are out of date at which point they will be destroyed according to institutional policies. Destruction will be documented in the Drug Accountability Record Form.

8.4 Personalized neoantigen peptides

8.4.1 Description

Personalized neoantigen peptides are comprised of up to 20 distinct peptides unique to each participant. Each peptide is a linear polymer of ~20 - ~30 L-amino acids joined by standard peptide bonds. The amino terminus is a primary amine (NH₂-) and the carboxy terminus is a carbonyl group (-COOH). Only the standard 20 amino acids commonly found in mammalian cells are utilized (alanine, arginine, asparagine, aspartic acid, cysteine, glutamine, glutamic acid, glycine, histidine, isoleucine, leucine, lysine, methionine, phenylalanine, proline, serine, threonine, tryptophan, tyrosine, valine). The molecular weight of each peptide varies based on its length and sequence and is calculated for each peptide.

8.4.2 Form

The two peptide pools, each containing up to 10 peptides, will each be provided in one bulk aliquot for use in Drug Product preparation; they will be packaged with a tamper evident seal, labelled and shipped under appropriate temperature controlled conditions to DFCI Pharmacy dept.

Bulk aliquots for up to 2 different peptide pools will be identified with the patient's Study ID number (i.e. 18279-101). Final sterile filtration will be performed by the Pharmacy department prior to aliquoting into vials. The vials containing peptide pools are to be stored at -70°C or colder until use.

8.4.3 Storage and Stability

Personalized neoantigen peptides are to be stored at the DFCI Pharmacy at a temperature of -70°C or colder. The thawed vials and the final mixture of personalized neoantigen peptides, poly-ICLC, and Montanide can be kept at room temperature but should be used as soon as possible after preparing the peptide + poly-ICLC + Montanide mixture.

8.4.4 Compatibility

Personalized neoantigen peptides will be mixed with poly-ICLC just prior to use to prepare the final product (NeoVax plus Montanide).

8.4.5 Handling

There are no specific instructions for handling personalized neoantigen peptides.

8.4.6 Availability

The personalized neoantigen peptides are prepared by a GMP facility under contract with DFCI and will be supplied directly to the DFCI. No other institutions will be involved in delivering personalized neoantigen peptides under this protocol.

8.4.7 Preparation

[REDACTED]

[REDACTED]

[REDACTED]

8.4.8 Administration

Following mixing with personalized neoantigen peptides, the personalized neoantigen vaccine is to be administered subcutaneously.

8.4.9 Ordering

The order for personalized neoantigen peptides to the peptide vendor will be placed by the DFCI separately for each individual participant. Delivery time is anticipated to be 4 – 8 weeks.

8.4.10 Accountability

The investigator, or a responsible party designated by the investigator, should maintain a careful record of the inventory and disposition of the agent using the NCI Drug Accountability Record Form (DARF) or another comparable drug accountability form. (See the NCI Investigator's Handbook for Procedures for Drug Accountability and Storage.)

8.4.11 Destruction and Return

At the end of the study, after a patient finishes treatment, or after a patient discontinues treatment early, unused supplies of personalized neoantigen peptides will be released to the sponsor for further research or destroyed according to institutional policies. If unused personalized neoantigen peptides are destroyed, this will be documented in the Drug Accountability Record Form.

[figure not shown]
8.5 Montanide

8.5.1 Description

[REDACTED]

[REDACTED]

[REDACTED]

8.5.2 Form

Montanide ISA-51 VG is supplied by Seppic in 2R3 amber vials filled with 3 ml containing Montanide ISA-51 VG.

8.5.3 Storage and Stability

Montanide ISA-51 SG is stable at room temperature for 3 years from the date of manufacture. It is preferable to keep unused vials in the original styrofoam box at standard room temperature.

8.5.4 Compatibility

Montanide ISA-51 SG will be mixed with personalized neoantigen peptides and poly-ICLC just prior to use to prepare the final product (neoantigen vaccine).

8.5.5 Handling

There are no specific handling instructions for Montanide ISA-51 VG.

8.5.6 Availability

Montanide ISA 51 VG is an investigational agent and will be sourced as commercially available product from Seppic.

8.5.7 Required Supplies

I-connectors (luer lock adapters) used to facilitate emulsion preparation will also be supplied by the study.

8.5.8 Administration

Following mixing with the personalized neoantigen peptides, the vaccine (peptide + poly-ICLC + Montanide® ISA-51 VG) is to be administered subcutaneously.

8.5.9 Accountability

The investigator, or a responsible party designated by the investigator, should maintain a careful record of the inventory and disposition of the agent using the NCI Drug Accountability Record Form (DARF) or another comparable drug accountability form. (See the NCI Investigator's

Handbook for Procedures for Drug Accountability and Storage.)

8.5.10 Destruction and Return

At the end of the study, unused supplies of Montanide will be destroyed according to institutional policies. Destruction will be documented in the Drug Accountability Record Form.

8.6 Preparation of NeoVax + Montanide

A high-contrast, black and white image. The top portion is a dark rectangle. Near the top edge, there are three white, abstract shapes: two 'L' shapes pointing downwards and to the left, and one 'J' shape pointing downwards and to the right. The bottom portion is a white rectangle. At the very bottom edge, there is a small, dark, horizontal mark that looks like a stylized 'J' shape pointing upwards and to the left.

8.6.1 Preparing NeoVax A + Montanide vaccine

A series of five horizontal black bars of varying lengths, decreasing from left to right. The first bar is the longest, followed by a shorter one, then a very long one, then a medium one, and finally a short one. They are positioned against a white background.

A black and white photograph of a dark, rectangular object, likely a book or folder, resting on a light-colored surface. The object is centered in the upper half of the frame, with its top edge appearing slightly irregular or torn. The background is a plain, light color, providing a stark contrast to the dark object.

The image consists of six horizontal bars of varying lengths, rendered in black and white. Each bar is black on its left side and white on its right side. A small, black, step-like protrusion is located on the far left of each bar. The bars are arranged vertically, with the first bar being the longest and the last bar being the shortest. The background is white.

8.6.2 Preparing Pool B NeoVax + Montanide vaccine

A horizontal bar chart consisting of 10 bars. Each bar is a rectangle divided into two equal halves: the left half is black and the right half is white. The length of each bar increases progressively from left to right. The first bar is the shortest, and the tenth bar is the longest. The bars are separated by small gaps.

A large black rectangular redaction box covers the top portion of the page. Below this, there are several horizontal black bars of varying lengths, each redacting a block of text. The redaction bars are positioned in a staggered, non-overlapping manner across the page area.

[REDACTED]

[REDACTED]

[REDACTED]

[REDACTED]

8.6.3 NeoVax vaccine preparation without using Montanide

[REDACTED]

9. BIOMARKER, CORRELATIVE, AND SPECIAL STUDIES

9.1 Pharmacodynamic Studies

Immune monitoring will be performed in a step-wise fashion as outlined below to characterize the intensity and quality of the elicited immune responses. Peripheral blood and tumor will be collected serially at different time points as specified in the study calendar.

If sufficient tumor tissue is available, a portion of the tumor will be used to develop autologous melanoma cell lines for use in cytotoxic T-cell assays.

9.1.1 Screening *ex vivo* IFN- γ ELISPOT

For each participant, a set of screening peptides will be synthesized. The screening peptides will be 15-17 amino acids in length, overlapping by 11 amino acids and covering the entire length of each peptide or the entire length of the neoORF for neoORF-derived peptides. The set of participant-specific screening peptides will be pooled together (either as a single pool or in four sub-pools corresponding to the immunizing peptide pools) at approximately equal concentration and a portion of each peptide will also be stored individually. In addition, the predicted 9mer or 10mer epitope for each immunizing peptide will be synthesized and pooled. Purity of the peptide pools will be ascertained by testing PBMC from 5 healthy donors with established low background in *ex vivo* IFN- γ ELISPOTs. Initially, PBMC obtained prior to Nivolumab, prior to Vaccination, and at week 20 (the primary immunological endpoint) will be stimulated for 18 hours with the overlapping 15-17mer peptides (11 amino acids overlap) and with the 9mer/10mer epitopes to examine the global response to the peptide vaccine. Subsequent assays may utilize PBMC collected at other time points as indicated. If no response is identified at the primary immunological endpoint using the *ex vivo* IFN- γ ELISPOT assay, PBMC may be stimulated *in vitro* with the peptide pool for a longer time period (up to 10 days) and re-analyzed.

9.1.2 Deconvolution of epitopes in follow-up *ex vivo* IFN- γ ELISPOT assays

Once an IFN- γ ELISPOT response elicited by an overlapping or epitope peptide pool is observed (defined as at least 55 spot forming units / 10^6 PBMC or increased at least 3 times over baseline), the particular immunogenic peptide eliciting this response will be identified by de-convoluting the peptide pool into sub-pools based on the immunizing peptides and repeating the *ex vivo* IFN- γ ELISPOT assays.

In some cases, it may be necessary to synthesize additional peptides to precisely characterize the stimulating epitope.

9.1.3 Additional assays to be conducted on a case-by case basis for appropriate samples

- The entire 15-17mer pool or sub-pools will be used as stimulating peptides for intracellular cytokine staining assays to identify and quantify antigen-specific CD4⁺, CD8⁺, central memory and effector memory populations.
- Similarly, these pools will be used to evaluate the pattern of cytokines secreted by these cells to determine the T_H1 vs T_H2 phenotype.
- Fluorescent-labeled tetramers may be prepared for direct flow-cytometric characterization of responding CD8⁺ T cells to directly track and measure the size of T cell populations responding to neoantigens.
- If a melanoma cell line is successfully established from a responding participant and the activating epitope can be identified, T-cell cytotoxicity assays will be conducted using the mutant and corresponding wild type peptide reactive T cells against the autologous tumor cell line.
- Single cell RNA-Seq analysis from pre- and post-treatment tumor samples to assess the activation states of T cells and other immune cells.
- Single cell sequencing of both TCR V α and V β subunits in serially collected peripheral blood and tumor samples collected before and after Nivolumab and vaccination, to characterize the global changes in TCR repertoire following vaccination as well as to track individual T cell clones over time in relation to vaccination.

9.1.4 Immunohistochemistry

Immunohistochemistry of tumor samples will be conducted to assess PD-L1 expression by tumor cells and tumor infiltrating immune cells and to quantify immune infiltrates such as CD4⁺, CD8⁺, MDSC, and Treg infiltrating populations.

9.2 Future Analyses

We may amend this protocol at a future date should we decide to conduct additional analyses utilizing future-generated samples from study participants (e.g. additional surgeries and autopsy tissue). Patients consenting to this trial agree to allow access to these future-generated samples.

10. STUDY CALENDAR

Procedure ¹	Screen ²	Pre-Treatment ³	Pre-Vaccination Treatment				Vaccination Treatment								Post Vaccination		Follow Up ¹⁴
			0	4	8	10	12	13	15	16	18	19	20	21	22	24	Q4 weeks
Week	NA																
Informed Consent	X																
Med Hx	X																
Concomitant Medication	X	X	X	X	X	X	X	X	X	X	X	X	X	X	X	X	X
PE/Vitals/Pulse Ox	X		X	X	X	X	X	X	X	X	X	X	X	X	X	X	X
ECOG PS	X		X	X	X	X	X	X	X	X	X	X	X	X	X	X	X
Staging scans ³	X						X									X	X
CBC w/ diff	X		X	X	X	X	X	X	X	X	X	X	X	X	X	X	X
Serum Chem ⁴	X		X	X	X	X	X	X	X	X	X	X	X	X	X	X	X
12-lead EKG	X																
Pregnancy Testing ⁵	X		X	X		X	X		X		X						
Thyroid Stimulating Hormone ⁶	X																
Infectious Panel ⁷	X																
Urinalysis	X																
Blood draw for vaccine manufacturing ⁸	X																
HLA class I and II typing ⁹		X															
Nivolumab administration ¹⁰			X	X	X		X			X			X		X	X	X
Ipilimumab administration ¹¹																	
Neoantigen vaccine Administration ¹²																	
Tumor biopsy ^{11,*}		X ¹¹													X ¹¹		
Leukapheresis ^{12,*}		X ¹²													X ¹²		
Blood draw for immune response monitoring ^{13,*}			X ¹³		X ¹³										X	X	
Vaccine biopsy [*]																	
Adverse Events			X	X	X	X	X	X	X	X	X	X	X	X	X	X	X

*please see Vaccine + Ipilimumab administration and vaccine-related assessments table below

- 1 All study procedures should be performed within +/- 3 day window unless specified otherwise
- 2 Screening assessments must be completed within 30 days of, and prior to the first dose of Nivolumab on Week 0 Day 1. An additional 15 days is allowed for a repeat biopsy, if needed, to obtain adequate tissue for sequencing. This initial biopsy sample should have approximately 30% tumor cellularity and a minimum of 5-8 cores or 100 mm³ in order for sequencing to be completed
- 3 +/- 14 day window for staging scans CT or MRI of other areas of disease (e.g. neck) should be obtained as clinically indicated. If IV contrast is contraindicated, a non-contrast CT and MRI may be used to evaluate sites of disease where a CT without contrast is not adequate. The imaging modality should remain consistent throughout the study and should be the same modality used at Screening. Photographs should be taken of one non-biopsied representative skin lesion, if feasible, on the same day that radiographic scans are obtained. The 100 day CT/MRI can be obtained within a +/-30-day window. If a patient has undergone a procedure (CT or MRI) that is within the allotted timeframe for evaluation, then the patient does not have to undergo an additional procedure. Clinical assessments must be based on RECIST v1.1. After the week 24 timepoint, staging scans should be performed every 12 weeks
- 4 Glucose, urea nitrogen, creatinine, sodium, potassium, calcium, total and direct bilirubin, AST, ALT, alkaline phosphatase
- 5 Women of childbearing potential (WOCBP) must have a negative serum or urine β -HCG pregnancy test. Urine or serum pregnancy test should be at screening, within 24 hours prior to receiving the first dose of study medication and then every 4 weeks while on treatment.
- 6 Thyroid stimulating hormone with reflex T4
- 7 HBsAg, HBcAb, HCV, HIV I/II Ab
- 8 At least two 10mL EDTA tubes will be collected for vaccine production purposes. The tubes will be kept frozen at the CRL until the day of shipment for DNA sequencing
- 9 Molecular HLA typing to be performed by Tissue Typing Laboratory (HLA-A, HLA-B, HLA-C, and HLA-DR)
- 10 Nivolumab treatment will start within 2 weeks of tumor biopsy and once histopathology report confirms melanoma and the biopsy sample is confirmed to have adequate tumor content for DNA sequencing. Nivolumab dosing every 4 weeks (+/- 3 days) until disease progression or intolerable toxicity (minimum 26 days between dosing). Nivolumab will be administered until intolerable toxicity, disease progression (unless treatment beyond progression is deemed to be beneficial for the patient) for a maximum duration of 24 months
- 11 Tumor biopsies will be collected in patients with unresectable melanoma who have metastatic sites accessible to serial tumor biopsies within two weeks prior to Nivolumab treatment initiation. Tumor biopsy must contain $\geq 30\%$ of tumor cells. At a minimum, 5 core biopsies or a surgical tumor specimen of 100mm³ will be obtained. Skin punch biopsies of a skin lesion are also allowed. The collection of tumor biopsies for research purposes do not apply for patients with stage III melanoma
- 12 Leukapheresis procedure will be performed within 14 days before starting Nivolumab. At each Leukapheresis collection timepoint 2x10 mL EDTA tubes will be collected. These tubes should be dropped off at the IAL upon collection. If Leukapheresis cannot be performed a total of 200mL of blood should be drawn. If starting of vaccine administration gets delayed, week 20 leukapheresis will be collected before vaccination timepoint #4. A Leukapheresis during the Post-Vaccination treatment/ Followup period may be performed
- 13 Unless otherwise specified, 80 mL of blood will be drawn for immune monitoring.
- 14 Active Follow-Up: Participants removed from active study treatment will be followed at the following schedule until initiation of a new therapy for recurrent disease, withdrawal of consent, or death (whichever comes first):
 - At least every 3 months (+/- 2 weeks) for the first 2 years after initiation of study therapy,
 - At least every 4 months (+/- 2 weeks) for the third year after study therapy initiation,
 - At least every 6 months (+/- 4 weeks) thereafter, until 5 years have passed since study therapy initiationLong-Term Follow-Up: Participants removed from active follow-up for progression/initiation of a new therapy will enter long-term follow-up, where they will be followed via medical record review until death for survival. Updates to the CRFs are to be made approximately every six months
- * Please see table below

Neoantigen vaccine + Ipilimumab administration calendar and assessments related to vaccination timepoints

Procedure ¹	Pre-vaccine assessments	Neoantigen Vaccine Dose #1 ^c	Post vaccine dose 1 visit	Neoantigen Vaccine Dose #2 ^c	Post vaccine dose 2 visit	Neoantigen Vaccine Dose #3 ^c	Post vaccine dose 3 visit	Neoantigen Vaccine Dose #4 ^c	Post vaccine dose 4 visit
PE/vitals Concomitant Medications ECOG, CBC w/ diff, Serum Chemistry ²		X	X	X	X	X	X	X	X
Leukapheresis	X ^a							X ^a	
Tumor biopsy	X ^b							X ^b	
Blood draw for immune response monitoring			X ^d	X ^d		X ^d			X ^d
Neoantigen vaccine administration		X				X		X	
Ipilimumab administration		X				X		X	
Vaccine site skin biopsy						X ^c			

a Leukapheresis procedure will be performed at the following timepoints:

- within 14 days before first vaccination timepoint #1
- within 7 days before vaccination timepoint #4

At each Leukapheresis collection timepoint 2x10 mL EDTA tubes will be collected. These tubes should be dropped off at the IAL upon collection

NOTE: If Leukapheresis cannot be performed a total of 200mL of blood should be drawn. If starting of vaccine administration gets delayed, week 20 leukapheresis will be collected before vaccination timepoint #4.

b Tumor biopsies will be collected at the following timepoints:

- within two weeks before starting the neoantigen vaccine Dose #1
- within two weeks prior to neoantigen vaccine Dose #4
- at the time of progression

At a minimum, 5 core biopsies or a surgical tumor specimen of 100mm³ will be obtained. Skin punch biopsies of a skin lesion are also allowed

c Expected neoantigen vaccine administration timepoints (see below). If there is a delay in vaccine preparation, Dose #1 should be administered as soon as the neoantigen vaccine is available. Doses #2, #3, and #4 should be scheduled every 3 weeks after Dose #1:

- neoantigen vaccine Dose #1: Week 12
- neoantigen vaccine Dose #2: Week 15
- neoantigen vaccine Dose #3: Week 18
- neoantigen vaccine Dose #4: Week 21.

If neoantigen vaccine administration coincides with nivolumab administration, neoantigen vaccine + Ipilimumab will be administered before Nivolumab

d Unless otherwise specified, 80 ml of blood will be drawn for immune monitoring. Blood collections will be performed at the following timepoints:

- one week (+/- 3 days) after neoantigen vaccine Dose #1
- before neoantigen vaccine Dose #2
- before neoantigen vaccine Dose #3
- within 3 weeks (+/- 3 days) after neoantigen vaccine Dose #4
- before each nivolumab administration during the post vaccination period

e Skin biopsies near vaccine injection sites (two 5 mm punch biopsies) should be performed at the following timepoints:

- prior to neoantigen vaccine Dose #3,
- between 48-72 hours after neoantigen vaccine Dose #3

Additionally, if a different vaccine site appears to clinically have a higher degree of inflammation, additional punch biopsy (two 5mm) of that site may be taken.

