5.2.1.3 Nivolumab Continuation Period

After neoantigen vaccine (NeoVax plus Montanide) / Ipilimumab treatment has been completed, patients with unresectable stage IIIB/C/D or IV melanoma will continue to receive Nivolumab alone at a flat dose of 480 mg as a 30 minutes (+/- 10 min.) i.v. infusion every 4 weeks (28 days), until disease recurrence or progression, unacceptable toxicity, or withdrawal of consent, for a maximum duration of up to 2 years from the first study treatment in the Run in Period. Participants with completely resected melanoma will receive nivolumab for a maximum period of one year (13 doses)

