5.7 Duration of Therapy / Criteria for Taking a Participant Off Protocol Therapy

Duration of therapy will depend on tolerability of the immunizations and evidence of disease recurrence or progression as judged by the treating investigator. In the absence of treatment delays due to adverse events, treatment will be given for two years in patients with unresectable melanoma and for one year (13 doses) for participants with stage III/B/C/D or IV completely resected melanoma, respectively, or until one of the following criteria applies:

- Disease progression or recurrence, if it is deemed by the treating investigator to be in the best interest of the participant to discontinue study treatment. If there is clinical or radiographic disease progression or recurrence prior to initiation of vaccine at week 12 or at the week 12 scan, treatment as per protocol (Nivolumab plus NeoVax + Montanide + local Ipilimumab) should be given unless deemed not in the best interest of the patient by the investigator.
- Intercurrent illness that prevents further administration of treatment
- Unacceptable adverse event(s)
- Participant demonstrates an inability or unwillingness to comply with protocol requirements
- Participant decides to withdraw from the study, or
- General or specific changes in the participant's condition which render the participant unacceptable for further treatment in the opinion of the treating investigator.

Participants will be removed from the protocol therapy when any of these criteria apply. The reason for removal from protocol therapy, and the date the participant was removed, must be documented in the case report form (CRF). Alternative care options will be discussed with the participant.

When a participant is removed from protocol therapy and/or is off of the study, the relevant Off-Treatment/Off-Study information will be updated in OnCore.

In the event of unusual or life-threatening complications, participating investigators must immediately notify the Principal Investigator, [name], PhD at DFCI [REDACTED]

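### The study calendar sets a single 24-month nivolumab maximum with no patient group named, while Sections 5.2.1.3 and 5.7 limit completely resected patients to one year

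*Protocol*

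**What the plan says.** Three places in the Protocol set the length of nivolumab treatment.

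- **Section 5.2.1.3 (Nivolumab Continuation Period)** separates two groups. After vaccination, "patients with unresectable stage IIIB/C/D or IV melanoma will continue to receive Nivolumab alone at a flat dose of 480 mg". The time limit for this group comes later in the same sentence: "for a maximum duration of up to 2 years from the first study treatment in the Run in Period". For the other group: "Participants with completely resected melanoma will receive nivolumab for a maximum period of one year (13 doses").
- **Section 5.7 (Duration of Therapy)** makes the same split. If adverse events cause no delay, unresectable disease is treated over two years, whereas the shorter period is stated as "for one year (13 doses) for participants with stage III/B/C/D or IV completely resected melanoma".
- **Section 10 (Study Calendar), footnote 10**, gives the schedule as "Nivolumab dosing every 4 weeks (+/- 3 days) until disease progression or intolerable toxicity" and then a single limit: "for a maximum duration of 24 months". It does not mention resection status and does not refer the reader to Section 5.2.1.3 or 5.7.

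Inclusion criterion 3.1.1.2 admits patients whose melanoma is already resected, as well as those with resectable or unresectable disease. The main calendar has one nivolumab row, which runs into the four-weekly column after vaccination. No other calendar footnote in the text gives a one-year limit.

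**The concern.** Staff commonly work from the calendar. Someone scheduling a completely resected patient from it would find a 24-month ceiling and nothing to suggest a shorter one; someone using the treatment sections would stop at 13 doses. The protocol as written therefore supports two different exposures for the same patient.

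Three things depend on this:

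- **Exposure and toxicity risk** in patients with no remaining measurable disease.
- **The safety window.** Non-serious adverse events are collected for at least 100 days after the last dose (Section 7.2.1), and serious events are reported to the drug supplier through 100 days after dosing stops (Section 7.5). Both end points move with the last dose.
- **The recurrence summary.** Progression or recurrence by disease status is a secondary endpoint (Protocol Sections 1.3 and 13.1; SAP, Secondary Endpoints). If the length of nivolumab differed among resected patients, their recurrence count would mix two treatment durations, in a very small group.

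**Working it through.** **Inputs**

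- Dosing interval: 28 days (Section 5.2.1.3; footnote 10).
- Maximum, completely resected: one year, 13 doses (Sections 5.2.1.3 and 5.7).
- Maximum, unresectable: two years (Sections 5.2.1.3 and 5.7).
- Maximum in footnote 10, no group named: 24 months.

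**Step 1: reproduce the plan's own figure.** 13 doses × 28 days = 364 days, or 52 weeks. With the first dose at week 0, dose 13 falls at 12 × 4 = week 48. One year and 13 doses agree with each other.

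**Step 2: apply the same rule to 24 months.** 24 × 365.25 / 12 = 730.5 days, and 730.5 / 28 = 26.1, so there are 26 full cycles and 26 doses. A 27th dose is possible if one is given on day 26 × 28 = 728, inside the limit.

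**Step 3: difference for a resected patient.** 26 − 13 = 13 doses, a ratio of 2. Counting every dose day that falls inside the limit gives 14 doses in 12 months (day 364 is before day 365.25) and 27 in 24 months, again a difference of 13.

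**Step 4: effect on the safety window.** Dose 13 falls on day 12 × 28 = 336, so 100 days later is day 436. Dose 26 falls on day 25 × 28 = 700, so 100 days later is day 800. The window ends 800 − 436 = 364 days later under the calendar's limit.

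**Step 5: effect on the primary endpoint.** Vaccination is planned from week 12. The DLT window is six weeks in Section 5.5 and seven in Section 13.1, so it closes at week 18 or 19 if vaccination starts on time, well before week 52. No DLT count, cohort decision or tabulated probability depends on the nivolumab maximum.

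**The three places side by side**

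| Group | 5.2.1.3 | 5.7 | Calendar footnote 10 |
|---|---|---|---|
| Unresectable | up to 2 years | 2 years | 24 months |
| Completely resected | 1 year (13 doses) | 1 year (13 doses) | 24 months, read as written |

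The unresectable row agrees throughout. The resected row does not.

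**The case against.** The best defence is that footnote 10 was written with unresectable patients in mind and lost its qualifier. Much of its wording fits that. It starts nivolumab within two weeks of a tumor biopsy, whereas Section 5.2.1.1 gives resected patients a separate rule counted from enrollment. It allows treatment past progression, which Section 5.9 confines to unresectable disease. Its 24 months equals the unresectable maximum.

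That may be how the sentence arose, but it does not settle how it reads. Footnote 11, the next one, says outright that it concerns unresectable melanoma, so the calendar names a population when it means to. If footnote 10 does cover only unresectable patients, the calendar gives resected patients no rule for starting or stopping nivolumab. Either reading calls for a correction.

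A second argument is that a ceiling does not oblige anyone to reach it: stopping a resected patient at one year complies with all three places, and a careful reader would apply the shorter limit. That is true, and it lowers the practical risk. It still leaves two different maxima for the same patients, and the text gives no rule on which section prevails.

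A third argument concerns scale, and it stands. Thirteen extra infusions is a worst case. It needs a site to follow the calendar against two explicit sections for a full further year, in a patient without recurrence or limiting toxicity. The SAP (Modified Design) reports that the expansion cohort never opened. If both escalation cohorts of five filled, about 10 patients were treated, and the documents do not say how many were resected. Recurrence is summarised descriptively, with no test between groups.

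**Conclusion.** The inconsistency is real. For completely resected patients the calendar's stated maximum is 24 months (26 doses, or 27 if one falls on day 728), against 13 doses in Sections 5.2.1.3 and 5.7. The potential excess is up to 13 infusions per patient, with the 100-day safety window ending up to 364 days later. These figures assume dosing every 28 days without delay and footnote 10 read as written.

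This is an internal inconsistency in an operational treatment rule and should be corrected. It does not threaten the primary endpoint. It bears on resected patients' exposure, their safety follow-up and the interpretation of their recurrence count. Nothing in the documents shows that anyone was treated beyond one year. Which duration is right is a clinical matter for the sponsor, and no view is taken here.

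**What to change.** Reconcile footnote 10 of the Study Calendar with Sections 5.2.1.3 and 5.7, so that one maximum is stated for each disease group and is the same wherever it appears. A cross-reference from the footnote to the treatment section would help keep the places aligned. This is a wording correction.

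Accrual has already stopped, so reporting matters at least as much as wording. Add to the SAP a descriptive table of nivolumab doses received and time from first to last dose, by disease group (completely resected, unresectable), shown beside the progression and recurrence counts. State whether any resected patient received more than 13 doses. The Statistical Analyses section of the SAP currently lists no exposure summary. Section 8.1.9 of the Protocol already requires drug accountability records, so no new data collection should be needed.
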